“Get Vaccinated!” provides prompts for participants to create a tailored HPV vaccination plan of when (i.e., target date) and where to get HPV vaccine and their reasons for wanting to get vaccinated (i.e., motivations). Thus, this section helps participants specify their HPV vaccine implementation intentions, an approach that improves goal achievement and engagement in health behaviors.⁵⁹ The resulting tailored HPV vaccination plan is available for printing/emailing (see Appendix for Summary Sheet).

Unidirectional vaccine reminders. Participants in the Out-U group will be sent monthly unidirectional reminders via text message/email about getting HPV vaccine (see Appendix). All

reminders for the Out-U group will be unidirectional, meaning that participants will not have the option to respond to reminders. Reminders will be sent via an automated process linked to the project website. The monthly reminders will start one month after randomization and continue for the 9-month follow-up period, as they can help promote both HPV vaccine initiation and completion.

2.g. Out-I Group. The Out-I group will receive the *Outsmart HPV* intervention that includes: a) population-targeted, individually-tailored content via the project website; and b) interactive text message/email vaccine reminders. The Out-I and Out-U groups will be identical except in the type of vaccine reminders sent to YSMM.

Population-targeted, individually-tailored content. Identical to the Out-U group (see Section 2.f.).

Interactive vaccine reminders. Participants in the Out-I group will be sent monthly tailored interactive reminders via text message/email about getting HPV vaccine (see Appendix). All reminders for the Out-I group will be interactive, meaning that participants will have the option to respond to obtain additional information that is tailored to their individual needs. As with the Out-U group, the monthly reminders will start one month after randomization and continue for the 9-month follow-up period.

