Communications for the interactive reminders will be sent through a combination of automated and manual processes, as described further below. To increase participant engagement, some of the interactive reminder texts will also contain a meme or brief animation in Graphics Interchange Format (GIF). Similar to the approach taken in other technology-based interventions with adolescents and young adults,³⁴ the memes and GIFs are intended to be funny or motivational and reinforce behavior.

For each month, the initial text sent to participants will be automated and include a question that prompts a response. Including a prompted message can increase participant responsivity compared to texts without unprompted messages.³⁵ Depending on how a participant responds to this initial communication, additional automated communications with information and resources will be sent to participants. Participants will then have the opportunity to text further questions they may have to the study team (participants can ask as many questions as needed). A study team member will review questions received and manually send an appropriate response, based on a library of example responses that has been developed for this study (see Appendix); responses for unanticipated questions will be discussed and agreed upon by the study team.

2.h. T2 Survey. Immediately after viewing intervention or control materials, participants will complete the T2 survey on the project website (about 10 minutes in duration; see Appendix). The T2 survey will assess theoretical constructs and satisfaction with study materials. Participants will not be able to access any study materials during the T2 survey. T2 survey completion will end the initial project website session. Participants will receive a \$40 gift card for completing the T1/T2 surveys. Incentives will be sent to participants via email (see Appendix).

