If, for some reason, a participant fails to complete all study activities up to this point, they will receive survey completion notifications (see Appendix for Survey Notifications) via email/text message. Survey completion notifications will be sent: 1) immediately after the participant leaves the project website; and 2) 2 days later if study activities have not yet been completed. Participants will have a maximum 3-day window to complete the study activities up to this point. If the 3-day window expires and a participant has not yet been randomized, they will not continue in the study. If the 3-day window expires and a participant has been randomized, they will continue in the study and be offered the opportunity to complete the T3 and T4 surveys.

2.i. T3 & T4 Surveys. Participants will complete the T3 and T4 surveys on the project website at 3 and 9 months after randomization. The T4 survey will occur 9 months later to allow participants ample time to receive all 3 doses of HPV vaccine. The T3 and T4 surveys are included in appendices.

Both the T3 and T4 surveys will take about 10 minutes and assess HPV vaccination status and theoretical constructs. The T4 survey will also assess satisfaction with study vaccine reminders (Out-

U and Out-I groups only). Participants will not be able to access any study materials during the T3 and T4 surveys. Participants will receive a \$20 gift card (sent via email) for completing the T3 survey and a \$35 gift card (sent via email) for completing the T4 survey (see Appendix).

If, for some reason, a participant fails to complete a survey it has been started, they will receive survey completion notifications (see Appendix for Survey Notifications) via email/text message. Survey completion notifications will be sent: 1) immediately after the participant leaves the project website; and 2) 2 days later if the survey has not yet been completed. Participants will have a maximum 3-day window to complete the survey once it has been started.

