Following completion of a participant's T4 survey or expiration of the 14-day T4 survey completion window (if the T4 survey is not completed), we will confirm HPV vaccination status via medical records (for those who completed an MRR form). A copy of the signed MRR form along with a request letter from the study team will be presented to a medical facility (via fax, phone, or secure email). The request letter will inform the facility about the study and request information from the medical record about the participant's HPV vaccination history be sent to the study team (via fax, phone, or secure email). Non-responding medical facilities will be contacted again by project staff.

2.k. Online Data Collection and Storage. As mentioned above, data from the MRR will be captured and managed via REDCap. REDCap is hosted by OSUWMC IT in the Ackerman Datacenter, and all data collected via REDCap is secured behind the OSUWMC firewall.

All other online data (e.g., from surveys, etc.) will be collected via the project website and stored by The Center for Health Communications Research (CHCR) at the University of Michigan.⁶³ CHCR ensures that data collection and storage processes are undertaken with attention to human subjects protections, respect for proprietary data, and maintaining integrity of the source data. CHCR was responsible for data storage and protection during our previous pilot study as well.

To ensure that the data are protected, CHCR uses virtualized servers provided by the University of Michigan Information Technology Services group. The virtualized servers are housed at two

redundant datacenters. These datacenters provide protection from lengthy outages, 24/7 staffing, restricted physical access, and disaster recovery. Virtual servers are backed up automatically onto encrypted tape for recovery and security. The datacenters also reduce the use of physical resources such as electricity and air conditioning.

All servers and the back-end databases are password protected. The server runs the Red Hat Enterprise Linux operating system and security patches and updates are downloaded and installed regularly. Each server is also protected by firewalls to restrict network access to the server. Additional details are available at <http://services.it.umich.edu/miserver/>.

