sexual minority (reports ever having oral or anal sex with a male or being sexually attracted to males; or identifies as gay, bisexual, or queer); d) lives in the US; e) has not received any doses of HPV vaccine; and f) did not participate in the pilot study. We will require men to read English and able to provide informed consent (inferred by completing the screener survey and consent form). All men will provide informed consent to participate in the RCT. The project website will provide participants with detailed information about the study prior to consent. For the RCT, participants will also be asked to provide medical record release (MRR), allowing for confirmation of HPV vaccination status during the study. The MRR form will be accessed through the project website and be managed using Research Electronic Data Capture (REDCap). A completed MRR form will not be required for study continuation.

2.b. Protection Against Potential Risk(s). Every means will be taken to minimize the risk associated with participating in this project. The autonomy of participants will be protected by informing all participants of the purpose of the study and allowing them to opt out of participation without repercuSSION. Participants will be able to withdraw from the study at any time, and they will be able to refuse to answer any question. Participants will be provided with study contact information in case they have any questions or concerns or experience any negative outcomes.

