This study will involve a randomized controlled trial of an HPV vaccine intervention for YSMM. Therefore, it will be registered in ClinicalTrials.gov. Throughout the ClinicalTrials.gov process, we will adhere to the policy recently released by the NIH. Specifically, we will: a) ensure registration to ClinicalTrials.gov occurs no later than 21 days after the first participant is enrolled into the randomized controlled trial; b) submit all required information during the registration process (descriptive, recruitment, location/contact, and administrative information); c) ensure results information is submitted no later than one year after the primary completion date of the randomized controlled trial; d) submit all required information during results reporting (participant flow information, demographics and baseline characteristics of enrolled participants, primary and secondary outcomes including results of any scientifically appropriate statistical tests, and adverse events); and e) update all submitted information once a year. Related, study team members will complete training in Good Clinical Practice (GCP) regarding clinical trials, as appropriate. This expectation was established by a recent policy statement from the NIH.

REFERENCES

6. National Cancer Institute. Surveillance, epidemiology and end results. <http://seer.cancer.gov/>. Updated 2014.

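### The protocol describes no question about harms that is the same in all arms, and Out-I has an extra staff-read text channel, so adverse-event counts may be incomplete and not comparable

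*Combined protocol and SAP*

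**What the plan says.** **How a harm becomes known.** Protection of Human Subjects, section 2.b, gives the same route to every arm: "Participants will be provided with study contact information in case they have any questions or concerns or experience any negative outcomes".

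**What the follow-up surveys cover.** Methods, section 2.i: "Both the T3 and T4 surveys will take about 10 minutes and assess HPV vaccination status and theoretical constructs". T4 adds satisfaction with the reminders, in the two reminder arms only.

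**How contact differs by arm.** In Out-U (Methods, section 2.f), "participants will not have the option to respond to reminders". In Out-I (section 2.g), after an automated monthly prompt and automated replies, "Participants will then have the opportunity to text further questions they may have to the study team". A team member reads these texts and answers them. Reminders go to Out-U and Out-I only. Controls receive survey notifications, as everyone does.

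**What is promised about adverse events.** The Data and Safety Monitoring Plan (Protection of Human Subjects, section 5) commits the team to monitoring participant safety and to handling known adverse events under the IRB's policy, with team review. Section 6 lists the content of the registry results submission, which includes "primary and secondary outcomes including results of any scientifically appropriate statistical tests, and adverse events". Neither section defines an adverse event or says how one is elicited.

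**The concern.** The plan says what happens to an adverse event once it is known, but not how the team would come to know of it beyond a man choosing to get in touch. Counts gathered that way depend on willingness and opportunity to report as well as on what happened. Opportunity is not the same in the three arms: Out-I men are prompted every month and can write to someone on the team, while Out-U men receive monthly messages on a thread that they cannot answer.

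Two readings of the published counts would be unsafe. A higher count in Out-I might reflect only its extra channel. A low count in Out-U might reflect only the lack of one. Few events overall might mean few harms, or few reports. The trial's stated efficacy outcomes do not depend on any of this.

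**Working it through.** The plan gives no expected adverse-event rate, no capture rate and no harms analysis, so it has no figure to reproduce. The check sets the described data sources side by side and then shows what unequal capture would do.

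**1. Does any described source ask about harms?** Protection of Human Subjects, section 1.b, names two sources of research material: online surveys and medical record review.

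- T1 (Methods, 2.c): background, health and the theory-based measures.
- T2 (2.h): "The T2 survey will assess theoretical constructs and satisfaction with study materials".
- T3 and T4 (2.i): vaccination status and the theory-based measures, with reminder satisfaction at T4 in the reminder arms.
- Medical records (2.j): the letter to the facility will "request information from the medical record about the participant's HPV vaccination history be sent to the study team", so this is not a source for harms.

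None of these, as described, asks about negative experiences. This cannot be confirmed item by item: "The T3 and T4 surveys are included in appendices", and the T1 and T2 instruments are in appendices too.

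**2. Opportunity to report, by arm**

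| Route | Control | Out-U | Out-I |
|---|---|---|---|
| Study contact information | yes | yes | yes |
| Monthly reminders from month 1 to month 9 | no | yes | yes |
| Reply thread read by staff | no | no | yes |

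The designated route is equal. The additional channel exists in one arm only.

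**3. Effect on counts.** For each arm, expected recorded events = N × true rate × capture probability, with N = 700 (Methods, 2.d). If the true rate is the same in every arm, N and the rate cancel, and the recorded ratio equals capture in Out-I divided by capture elsewhere. The rates below are assumptions. At a true rate of 2%, there are 700 × 0.02 = 14 events per arm:

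| Capture elsewhere | Capture in Out-I | Recorded elsewhere | Recorded in Out-I | Ratio |
|---|---|---|---|---|
| 30% | 30% | 4.2 | 4.2 | 1.00 |
| 30% | 50% | 4.2 | 7.0 | 1.67 |
| 30% | 70% | 4.2 | 9.8 | 2.33 |
| 10% | 50% | 1.4 | 7.0 | 5.00 |

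With 30% against 50% capture, a true rate of 1% gives 2.1 against 3.5 events, and 5% gives 10.5 against 17.5. If someone tested Out-I against another arm at two-sided 0.05, the chance of a significant result with no true difference would be about 9%, 13% and 27% at true rates of 1%, 2% and 5%. These come from a normal approximation, which is rough at such small counts, and the plan specifies no such test. The share of events missed is 1 − capture, so incompleteness follows from any capture below 100%.

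**4. A real difference could be mixed in.** The projected initiation rates (Methods, 2.m) give 700 × 0.20 = 140, 700 × 0.35 = 245 and 700 × 0.45 = 315 vaccinated men in control, Out-U and Out-I. If problems after vaccination are counted, true rates could differ by arm, and volunteered counts could not separate that from unequal capture.

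**5. Reach of a survey item.** With the 70% retention expected at 9 months (2.m), 0.70 × 700 = 490 men per arm would answer at T4, and 210 would not.

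**The case against.** The strongest reply is proportionality. The study is described as minimal risk (Protection of Human Subjects, 1.c), the monitoring plan scales its effort to risk, the team reviews risk and benefit monthly, and known events go to the IRB. Passive reporting is a defensible choice in that setting. This stands, and it limits the point to a minor one.

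The second reply is that the designated contact route is the same in all arms. The Out-I thread is for vaccine questions, and nothing says that harms will be logged from it. Unequal counts would require men to mention a harm there and staff to record it. This stands as a limit on certainty. It does not remove the difference in opportunity, and it shows that the plan leaves open what staff do when a harm is mentioned.

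Third, the survey instruments are unseen. A harm item, or a satisfaction item that brings out bad experiences, may exist. This stands, and the sponsor can settle it at once.

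A reader might go further and infer that harms will be under-counted and compared unequally, or that Out-I will show an excess of some stated multiple. The documents do not support this. The planned analyses cover efficacy, mediation and moderation, no comparison of harms by arm is specified, and any multiple only restates the capture rates that were assumed. Nor do they show that harms are likelier in the reminder arms. Section 1.c names uncomfortable survey topics and loss of confidentiality, expects no harm from what the reminders say, and controls also receive study messages.

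**Conclusion.** The point holds as a minor one. As described, the team learns of harms only when a man makes contact, no described survey content asks about them, and Out-I alone has a further channel read by staff. The promised adverse-event counts may therefore be incomplete, and any table by arm would rest on unequal opportunity to report.

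The size is not known. It is nil between arms if capture is equal. Otherwise, with equal true rates, it is the ratio of capture rates, which ran from 1.0 to 5.0 in the assumed scenarios tabulated above. The conclusion assumes that the survey appendices contain no harm item. Efficacy results are unaffected.

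**What to change.** First check the survey appendices. If no such item is there, add one identical question to T3 and T4 in all three arms: whether anything about taking part caused a problem (for instance distress, another person seeing a study message, or a problem after vaccination), with yes/no and free text.

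Then state how the reports will be used:

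- Report adverse events by arm with the source shown: solicited by survey, or volunteered by text, email or phone. This requires staff who answer Out-I texts to log any harm mentioned there.
- Base any comparison between arms on the solicited reports, with the number of responders in each arm as denominator.
- Keep all volunteered events in the reported totals, including those from men who did not answer T3 or T4. Otherwise a man who left after a bad experience would drop out of the table.

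The cost is one item in two existing online surveys and some extra, possibly unrelated, reports to process under the IRB policy. The remaining weakness is that the item misses non-responders, about 30% of men at 9 months on the plan's own expectation, so the comparison applies to responders only.
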